## 8.0 STUDY ENDPOINT and DATA ANALYSIS

### 8.1 Primary Endpoints: Primary endpoints consisted of the following:

Safety: The primary safety endpoint is the occurrence of reported unanticipated problems involving risk to subjects or others (“UPIRTSOs”). These UPIRTSOs are defined as those problems which alter the risks to subjects or others. This includes any study suspensions or holds. The primary safety endpoint analyses will be based on a risk-benefit conclusion.

Effectiveness: The primary effectiveness endpoints are an overall change in median reported symptoms of pain, anxiety, depression, and/or sleeplessness via numeric rating scales at 8 weeks. This primary effectiveness is measured by median reported symptom changes in pain, anxiety, depression, and/or sleeplessness for respective stratified populations via the following validated tools: Pain - Pain Intensity and Interference (PEG\_Scale), Anxiety - Generalized Anxiety Disorder 7-item (GAD-7) scale, Depression - Patient Health Questionnaire (PHQ-9), Sleeplessness - PROMIS short form 4a, and overall improvement of quality of life (QOL) - Patient’s Global Impression of Change (PGIC).

The hypothesis-driven criterion of effectiveness is to show that there is a statistically significant reduction in the median reported pain, anxiety, depression, and/or sleeplessness levels of patients using the Nu-V3 device. The second criterion is intended to show that there is a statistically significant improvement in reported quality of life and perceived treatment benefit, secondary to overall reported symptom reductions of pain, anxiety, depression, and/or sleeplessness.

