## 4.0 STUDY PROTOCOL

The Nu-V3 Clinical Study is a prospective, single-arm, open-label, multi-center study using the Nu-V3 cranial nerve stimulation treatment device in patients with pain, anxiety, depression, and/or sleeplessness.

For this Phase I study, a total of 50-100 patients at multiple centers will be registered for study participation. Study participants are those who have signed the informed consent form, met the inclusion and exclusion criteria, and are enrolled in the study at one of multiple sites. Enrolled participants are stratified based on their pain, anxiety, depression, and/or sleeplessness symptom presentation at baseline and treated with the Nu-V3 device for 8 weeks, then observed for an additional 4 weeks. Interim analysis of reported data will be based on baseline stratifications and conducted at 4, 8, and 12 weeks during this time. Post study, participants will be given the chance to continue with an optional maintenance treatment with the Nu-V3 device per a 2-weeks on, 2-weeks off schedule, for an additional 12 weeks, with an 8-week observation.

Subjects enrolled onto the Nu-V3 Clinical Trial will undergo the following regimen:

- At the baseline visit, patients will be asked to complete study questionnaires (Appendix 11) regarding all of the following symptoms: pain, anxiety, depression, and/or sleeplessness, as well as their quality of life, active medications, medical history, and demographical information.
- At each subsequent visit, patients will be asked to complete study questionnaires regarding all the following symptoms: pain, anxiety, depression, and/or sleeplessness, as well as their activity level and quality of life.
- The sessions will begin with the Nu-V3 device being placed on the left ear and three small pads (non-invasive) being placed on the ear. Each Nu-V3 device

lasts for up to 14 days with a change in the pads approximately 7 days into the treatment.

- Each session takes approximately 15-20 minutes. The placement of the device takes approximately 5 minutes and the remaining time is spent verifying ePRO form completion, and evaluating the patient for all device effects.
- The Nu-V3 device is mobile and is worn externally on the left ear 24 hours a day during treatment, fitting comfortably behind the ear. An electrical signal is sent to the external ear through coated wire leads attached to the device and adhesive pads which attach to three sites on the ear.

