Primary Endpoints: Primary endpoints consisted of the following:

1. **Safety:** The primary safety endpoint was the occurrence of reported unanticipated problems involving risk to subjects or others (“UPIRTSOs”). These UPIRTSOs are defined as those problems which alter the risks to subjects or others. This includes any study suspensions or holds. The primary safety endpoint analyses were based on a risk-benefit conclusion.
2. **Effectiveness:** The primary effectiveness endpoints were overall reduction in median reported symptoms of pain, anxiety, depression, and/or sleeplessness via numeric rating scales at 8 weeks. This primary effectiveness is measured by median reported symptom reductions in pain, anxiety, depression, and/or sleeplessness via the following validated tools: Pain intensity and interference- PEG Scale, Anxiety- Generalized Anxiety Disorder 7-item (GAD-7) scale, Depression- Patient Health Questionnaire (PHQ-9), Sleeplessness- PROMIS short form 4a, and overall improvement of quality of life (QOL) - Patient’s Global Impression of Change (PGIC).

The patient’s perceived treatment benefit and device comfort information, will be captured via the non-validated tool, Perceived Treatment Benefit Form (PTB-7). This effectiveness tool will measure median levels of reported perceived treatment benefit and device comfort.

The hypothesis-driven criterion of effectiveness was to show that there was a statistically significant reduction in the median reported pain, anxiety, depression, and/or sleeplessness levels of patients using the Nu-V3 device. The second criterion was intended to show that there was a statistically significant improvement in reported quality of life and perceived treatment benefit secondary to overall reported symptom reduction of pain, anxiety, depression, and/or sleeplessness.

Secondary Endpoints: Secondary endpoints consisted of the following:

1. **Effectiveness:** The secondary effectiveness endpoint was overall reduction in median reported symptoms of pain, anxiety, depression, and/or sleeplessness via numeric rating scales at 4, 8, and 12 weeks. This was measured via the following validated tools: Pain intensity and interference- PEG Scale, Anxiety- Generalized Anxiety Disorder 7-item (GAD-7) scale, Depression- Patient Health Questionnaire (PHQ-9), Sleeplessness- PROMIS short form 4a, and overall improvement of quality of life- Patient’s Global Impression of Change (PGIC).

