Risks to Health: Potential unanticipated problems require prompt reporting to Aspire IRB. These problems potentially place subjects or others at greater risk of physical or psychological harm than was previously recognized, and warrant consideration of substantive changes in the protocol or informed consent process or other action in order to protect the safety, welfare, or rights of participants. Aspire IRB must be notified within 5 calendar days of the event. The completed IRB Unanticipated Problem form (Appendix 3) must be received by Aspire IRB within 10 calendar days of the event. Unanticipated problems are defined as those problems which alter the risks to subjects or others. This includes any study suspensions or holds. This form will be used to report any problem that is unforeseen or involves risk. One form will be used per event or problem.

Table 4.1: Unanticipated Problems Involving Risk to Patients or Others			
	Phase I	Phase II	Total
UPIRTSO 1 (number)			
UPIRTSO 2 (number)			
UPIRTSO 3 (number)			
Overall UPIRTSOs Reported			

Table 4.2: Risk/ Mitigation Measures	
Identified Risk	Mitigation Measures

Insert Safety Analysis Here

Section 5.0: Results

Results: The principal safety and effectiveness results from patients in the Nu-V3 study are provided below. The primary safety analysis was based on all patients registered and included all reported UPIRTSO events. The primary safety endpoint included imputation for missing clinical outcomes data using the logistic regression method. The imputation model included baseline characteristics including age, sex/gender, marital status, primary language spoken, race/ethnicity, education history, and veteran status.

Primary Safety Endpoint:

Insert Primary Safety Endpoint Statistical Analysis

Insert Primary Safety Endpoint Statistical Table

Primary Effectiveness Endpoint:

Insert Primary Effectiveness Endpoint Statistical Analysis

Insert Primary Effectiveness Endpoint Statistical Table- 8 weeks

Secondary Effectiveness Endpoint:

Insert Primary Effectiveness Endpoint Statistical Analysis

Insert Primary Effectiveness Endpoint Statistical Table: 4, 8, 12 weeks

Sub-Analyses:

Insert Sub-Analyses Statistical Analysis

Insert Sub-Analyses Statistical Tables

Special Controls:

Insert Special Control Section Here

Benefit/Risk Determination:

Insert Benefit/Risk Section Here

Section 5.0: Administrative Information

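### The primary safety endpoint is to be analysed through a risk-benefit conclusion, which lets an uncontrolled effectiveness result into it; no safety-only estimate or interval is stated

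*Protocol*

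**What the plan says.** Protocol 8.1 names a countable safety variable: "The primary safety endpoint is the occurrence of reported unanticipated problems involving risk to subjects or others". Study suspensions and holds are included. The same paragraph then gives the basis for analysis: "The primary safety endpoint analyses will be based on a risk-benefit conclusion". The SAP, under Primary Endpoints, item 1, says the same: "The primary safety endpoint analyses were based on a risk-benefit conclusion".

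Section 5.0 (Results) of the SAP adds two details. The analysis set is given as "The primary safety analysis was based on all patients registered and included all reported UPIRTSO events", and missing data are handled as follows: "The primary safety endpoint included imputation for missing clinical outcomes data using the logistic regression method". The method itself is a placeholder, "Insert Primary Safety Endpoint Statistical Analysis". Further down the same section a Benefit/Risk Determination appears under its own label, also unfilled: "Insert Benefit/Risk Section Here".

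Section 4.0 (Safety) of the SAP contains Table 4.1, a shell with one row per UPIRTSO and an overall row, in columns for Phase I, Phase II and Total. The cells are numbers of events. Protocol 4.0 describes the design: "The Nu-V3 Clinical Study is a prospective, single-arm, open-label, multi-center study".

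**The concern.** The occurrence of UPIRTSOs can be estimated without knowing anything about symptom scores. A risk-benefit conclusion cannot be reached that way, because it needs the effectiveness result as an input. Here that result is a reduction in median self-reported scores with no control group, a change that regression to the mean or expectation can also produce. Neither document says how benefit is to be weighed against harm, who does it, or against what limit. Effectiveness does have a stated criterion, a statistically significant reduction, while safety has none of its own.

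Two things are at stake. The safety conclusion may be coloured by a favourable but uncontrolled symptom result, in a study that the SAP presents as pivotal support for a De Novo request. Separately, a bare count of events shows no uncertainty, so a reader cannot tell how large a risk the study leaves open.

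**Working it through.** **The passages compared.** The plan gives no UPIRTSO rate, acceptable limit, hypothesis or interval for safety, so there is no figure to reproduce.

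- Variable: occurrence of reported UPIRTSOs (Protocol 8.1; SAP Primary Endpoints, item 1).
- Basis of analysis: a risk-benefit conclusion (same two places).
- Analysis set: all registered patients (SAP Section 5.0).
- Missing data: logistic-regression imputation (SAP Section 5.0). This presupposes a yes/no outcome per patient.
- Estimate, interval and criterion: none stated. The relevant slots in SAP Sections 4.0 and 5.0 are unfilled.
- Benefit-risk weighing: a separate, unfilled section (SAP Section 5.0).

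The risk-benefit sentence is therefore the only stated basis for judging the endpoint. It sits awkwardly with the SAP's own layout, which gives benefit-risk a separate place.

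**What an interval would show.** Sample sizes are 50 to 100 for Phase I (Protocol 4.0) and 150 to 300 for both phases (SAP outcome templates; 50 + 100 = 150 and 100 + 200 = 300). For 0 patients affected out of n, the exact two-sided 95% upper limit is 1 − 0.025^(1/n):

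- n = 50: 1 − 0.025^(1/50) = 0.0711, or 7.1%
- n = 100: 1 − 0.025^(1/100) = 0.0362, or 3.6%
- n = 150: 1 − 0.025^(1/150) = 0.0243, or 2.4%
- n = 300: 1 − 0.025^(1/300) = 0.0122, or 1.2%

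For x > 0 patients affected, the exact (Clopper-Pearson) upper limit is the 97.5% point of a beta distribution with parameters x + 1 and n − x. With x = 1 it is 10.65% for n = 50 and 5.45% for n = 100.

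**Chance of seeing nothing.** The documents give no expected risk, so 2% and 3% are assumptions for illustration. The chance of no affected patient is (1 − p)^n:

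- p = 2%: 0.98^50 = 0.36 and 0.98^100 = 0.13
- p = 3%: 0.97^50 = 0.22 and 0.97^100 = 0.05

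These figures measure what a count without an interval leaves out. They depend on sample size alone and would be the same if the risk-benefit sentence were deleted. They are not an estimate of how far benefit might offset harm.

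**The case against.** The strongest reply is that the sentence is vague rather than wrong, and that the SAP in practice keeps safety apart. It has its own safety section with a UPIRTSO table, a risk and mitigation table and a slot for a safety analysis. Section 5.0 reserves a further statistical analysis and table for the primary safety endpoint. Events must reach the sponsor within 24 hours and the central IRB within 5 calendar days (Protocol 7.0), whatever the symptom scores show.

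Much of this stands, and it rules out several stronger readings:

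- A reader might infer that the endpoint cannot fail, or that benefit will be allowed to outweigh harm. The documents say neither; they leave the weighing undefined.
- A reader might infer that safety is never looked at by itself. The separate safety section and reserved tables count against that, although they are empty.
- A reader might infer that benefit and risk are weighed twice. The phrase in Protocol 8.1 may simply point to the Benefit/Risk Determination.
- A reader might infer that zero events will be reported as no risk. Table 4.1 is a blank shell, and nothing in the text says so.
- A reader might infer a lapse in oversight. The point concerns how the endpoint is analysed, not how events are reported.

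The objection does not remove the sentence itself. It appears in both documents as the basis of the primary safety analysis, and none of the reserved slots supplies an estimate or interval to stand in its place.

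**Conclusion.** The point holds as a weakness in a stated method, and it should be corrected. Tying the primary safety endpoint to a risk-benefit conclusion admits an uncontrolled, open-label effectiveness result into it, when a safety-only estimate is available at little cost and the SAP already has a place for the weighing. Nothing shows that harm would in fact be offset, so no size can be put on that part.

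The part with a size is the missing interval. With nobody affected, Phase I could not exclude a risk below 7.1% (n = 50) or 3.6% (n = 100), and the combined phases could not exclude one below 2.4% (n = 150) or 1.2% (n = 300). These limits assume independent patients, one yes/no outcome each, and all registered patients in the denominator. Patients who leave early with no report would count as unaffected, so the true uncertainty may be larger.

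**What to change.** Replace the risk-benefit sentence in Protocol 8.1 and in the SAP's Primary Endpoints, item 1, with:

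*The primary safety analysis is the number and percentage of registered patients with at least one reported UPIRTSO, with exact 95% confidence interval, based on observed events and interpreted without reference to effectiveness; UPIRTSOs involving others and study suspensions or holds are counted and listed separately.*

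Three further changes make the SAP consistent with this:

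- Add the denominator, percentage and interval to Table 4.1.
- Move the logistic-regression imputation in Section 5.0 to a sensitivity analysis.
- Keep the weighing of benefit against risk only in the Benefit/Risk Determination.

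The wording keeps the SAP's registered-patient set. It also keeps problems involving others and suspensions or holds in view; a patient percentage alone would drop them because they are not patient-level. It sets no pass/fail limit. If the sponsor wants one, it should be fixed before data are seen.

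The cost is one sentence in each document, a fuller table with a separate listing, and a reworded imputation paragraph. No new data are needed. The safety statement will carry its upper limit and so read slightly less favourably.

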## PHQ-9- Patient Health Questionnaire

Subject ID: \_\_\_\_\_ Date (dd/mmm/yyyy): \_\_\_\_/\_\_\_\_/\_\_\_\_

Over the last 2 weeks, how often have you been bothered by any of the following problems?  
(use "✓" to indicate your answer)

	Not at all	Several days	More than half the days	Nearly every day
1. Little interest or pleasure in doing things	0	1	2	3
2. Feeling down, depressed, or hopeless	0	1	2	3
3. Trouble falling or staying asleep, or sleeping too much	0	1	2	3
4. Feeling tired or having little energy	0	1	2	3
5. Poor appetite or overeating	0	1	2	3
6. Feeling bad about yourself—or that you are a failure or have let yourself or your family down	0	1	2	3
7. Trouble concentrating on things, such as reading the newspaper or watching television	0	1	2	3
8. Moving or speaking so slowly that other people could have noticed. Or the opposite — being so fidgety or restless that you have been moving around a lot more than usual	0	1	2	3
9. Thoughts that you would be better off dead, or of hurting yourself	0	1	2	3

add columns  +  +

(Healthcare professional: For interpretation of TOTAL, please refer to accompanying scoring card). TOTAL:

10. If you checked off any problems, how difficult have these problems made it for you to do your work, take care of things at home, or get along with other people?	Not difficult at all _____ Somewhat difficult _____ Very difficult _____ Extremely difficult _____
---	---

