## PATIENTS' GLOBAL IMPRESSION OF CHANGE (PGIC) SCALE

Subject ID: \_\_\_\_\_

Date (dd/mmm/yyyy): \_\_\_\_/\_\_\_\_/\_\_\_\_

Chief Complaint (Presenting Problem): \_\_\_\_\_

Since beginning treatment at this clinic, how would you describe the change (if any) in ACTIVITY LIMITATIONS, SYMPTOMS, EMOTIONS, and OVERALL QUALITY OF LIFE, related to your painful condition? Please circle the number below, that matches your degree of change since beginning care at this clinic for the above stated chief complaint.

No change	Almost the same	A little better	Somewhat better	Moderately better	Better	A great deal better
1	2	3	4	5	6	7

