**Explanation:**

- |  |  |
|--|--|
| 
 
1 = No change (or condition has got worse)
 
2 = Almost the same, hardly any change at all
 
3 = A little better, but no noticeable change
 
4 = Somewhat better, but the change has not made any real difference
 
 | 
 
5 = Moderately better, and a slight but noticeable change
 
6 = Better, and a definite improvement that has made a real and worthwhile difference
 
7 = A great deal better, and a considerable improvement that has made all the difference
 
 |
|--|--|

Patient's signature: \_\_\_\_\_

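### The PGIC is named as the quality-of-life endpoint, but its single rating cannot separate a quality-of-life gain from symptom relief

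*Protocol*

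**What the plan says.** Protocol section 8.1 gives the primary effectiveness endpoint at 8 weeks as four symptom scales (PEG, GAD-7, PHQ-9, PROMIS 4a) plus "overall improvement of quality of life (QOL) - Patient’s Global Impression of Change (PGIC". Its second effectiveness criterion is a "statistically significant improvement in reported quality of life and perceived treatment benefit, secondary to overall reported symptom reductions". Section 8.2 repeats both for weeks 4, 8 and 12. The SAP's primary and secondary endpoints follow the same pattern, and SAP Section 3.0 has a Quality of Life block whose outcome table is filled from the PGIC.

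The PGIC form in Appendix 11 asks "how would you describe the change (if any) in ACTIVITY LIMITATIONS, SYMPTOMS, EMOTIONS, and OVERALL QUALITY OF LIFE, related to your painful condition". The patient answers with one number: "Please circle the number below, that matches your degree of change since beginning care at this clinic for the above stated chief complaint". The lowest category reads "1 = No change (or condition has got worse".

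Section 4.0 says the baseline questionnaires cover the symptoms "as well as their quality of life, active medications, medical history, and demographical information". In section 4.1 the PGIC row starts at Week 2, and the list of patient-reported tools in footnote 3 contains no quality-of-life questionnaire.

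**The concern.** An endpoint called quality of life should rest on an answer about quality of life. Here that answer is one part of a four-part question with a single response, and two of the other parts, symptoms and emotions, overlap with what the four symptom scales already measure in the same primary endpoint. If the criterion is met, the report would say that quality of life improved significantly, and nothing collected could show whether that was so or whether patients were rating their symptoms again. What is at stake is one named element of the primary effectiveness result.

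**Working it through.** This is mainly a comparison of texts. The plan states no null value, test, significance threshold, effect size or power for the PGIC, so there is no figure to reproduce.

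**Step 1: the claim against the tool.**
- Claim (Protocol 8.1 and 8.2, SAP primary and secondary endpoints): a tested improvement in quality of life.
- Tool (Appendix 11, PGIC): change in "ACTIVITY LIMITATIONS, SYMPTOMS, EMOTIONS, and OVERALL QUALITY OF LIFE", with one circled number.
- Result: four domains and one score. No rule can recover the quality-of-life part.

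**Step 2: whether another tool fills the gap.** Footnote 3 of the schedule, in both documents, lists DQ-9, PTB-7, PEG, GAD-7, PHQ-9, PROMIS 4a and PGIC. None of the others is a quality-of-life instrument. PEG items 2 and 3 touch on enjoyment of life and activity, but as pain interference, and they are scored as pain.

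**Step 3: the baseline statement.** Section 4.0 promises quality of life at baseline. The PGIC has no Week 1 entry in its own row. Even if footnote 3 were read as placing it in the Week 1 packet, a rating of change since starting treatment gives no baseline level. The SAP's version of the baseline sentence lists activity level and omits quality of life, so the two documents also differ.

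**Step 4: illustration of how easily the criterion could be met.** These inputs are assumptions: a sign test against 1 (no change) with ratings of 1 dropped as ties, and two-sided alpha 0.05, which appears in the SAP only as a template example. The sample size of 50 to 100 is from section 4.0. Ratings cannot fall below 1, so every untied rating counts as improvement. With m such ratings, p = 2 × 0.5^m:
- m = 5: p = 0.0625
- m = 6: p = 0.031

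Six ratings above 1 suffice: 6/50 = 12% or 6/100 = 6% of patients. Let q be the share who rate 2 or more because of symptom relief only. The chance of significance is P(X ≥ 6) with X binomial (N, q):

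| q | N = 50 | N = 100 |
|---|---|---|
| 0.05 | 4% | 38% |
| 0.10 | 38% | 94% |
| 0.20 | 95% | over 99.9% |
| 0.30 | 99.9% | over 99.9% |

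If the form's 5-7 responder cut were instead tested against 50%, 33 of 50 or 61 of 100 responders would be needed. With a true responder share of 60% the chance is 24% or 46%; with 70% it is 78% or 98%. This bar is much higher, but those responders could still be rating symptoms only. The choice of test changes how easily the criterion is met. It does not change what the rating means.

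**The case against.** The strongest reply is that the plan claims less than the label suggests. Four parts of it deserve an answer.

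- **Independence.** A reader might infer that one effect is being counted twice as separate evidence. The documents do not support that. The second criterion calls the gain secondary to symptom reduction, so it is presented as following from symptom relief. This stands, and double counting is not the point made here.
- **Content.** A reader might infer that the PGIC does not address quality of life at all. The form names it in capitals, so a rating may well include it. This also stands. The defect is that the part cannot be separated.
- **The second component.** The criterion also asks for improvement in perceived treatment benefit, so the PGIC alone does not meet it. This does not rescue the label: PTB-7 item 1 asks how far the treatment helped the patient's symptoms, which symptom relief would also satisfy.
- **Consequence.** A reader might infer that the De Novo summary will state a quality-of-life benefit. The study objective and the SAP purpose name only the four symptoms, the SAP results text is blank, and the SAP table names the PGIC openly. That outcome is possible but not written.

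A hypothetical group with unchanged quality of life and a median PGIC of 5 or more would show little. It assumes its conclusion, and the 5-7 cut on the form is a note for reading one patient's score, not a group median. The Step 4 figures likewise assume the reason for the rating. They show what the criterion would permit, not what patients would do.

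**Conclusion.** The point holds as a mismatch between label and measure. The Protocol and SAP assign a tested quality-of-life endpoint to the PGIC alone, while the form yields one number for four domains. A significant result is compatible with symptom relief only and cannot be told apart from a quality-of-life gain. This follows from the wording of the form and the tool list and needs no numerical assumption. The percentages in Step 4 do depend on an assumed test, alpha and q, and are not figures from the plan.

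The effect is confined to the quality-of-life element of the primary and secondary effectiveness criteria. The four symptom endpoints do not depend on it.

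Two features of the form weaken the label further without carrying the point. The stem is tied to a painful condition although patients may enter with anxiety, depression or sleeplessness alone, and no change shares score 1 with worsening, so a loss of quality of life has no value of its own.

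**What to change.** 1. In Protocol 8.1 and 8.2, the SAP primary and secondary endpoints, and the SAP table now headed Quality of Life- PGIC with its associated figures, rename the endpoint *patient global impression of change*.
2. In the second criterion, in each place it appears, replace the improvement in reported quality of life with that term. Draw no quality-of-life conclusion from it. The renamed criterion still needs a stated null value and test.
3. Reconcile the quality-of-life statement in section 4.0 with the schedule and with the SAP's version: either remove it or name the tool and the visit.

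The cost is wording in two documents and the loss of quality of life as a primary claim. If the sponsor wants to keep that claim, it needs a separate instrument with a Week 1 assessment, which adds a questionnaire and an amendment.

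The difficulty questions that close the GAD-7 and PHQ-9 (for example "how difficult have these problems made it for you to do your work") are already in the ePRO set from Week 1, but they are not a substitute. They apply only if a problem was checked, and they refer to the anxiety or depression items. Any use should be optional, descriptive and limited to the anxiety and depression strata, with a stated rule for patients who check no problems.
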